Alexander et al compared four different smartphone application-based monitors: Instant Blood Pressure, Instant Blood Pressure Pro, Pulse Oximeter, and Pulse Oximeter Pro. Three different parameters were measured using these four devices: heart rate, blood pressure, and SpO₂. The comparison revealed a large degree of variance in the values between the Instant Blood Pressure, the Instant Blood Pressure Pro, the Pulse Oximeter, and the Pulse Oximeter Pro.⁹ Another study by Petersen and Dumont was conducted that compared the response of motion artifact of three different mobile pulse oximeter devices, all interfaced to Apple iPod Touch devices: the Nonin Xpod, the Masimo OEM inline module, and an Audio Phone Oximeter prototype. The study showed that there was more motion artifact at lower saturations for all three of the devices. The most valid measurements was found with Masimo's mobile device at readable values of approximately 85 to 87 percent.¹⁰

While the technology to detect SpO₂ and heartrates on smartphones is emerging and widely available, there is no evidence supporting its use in patients with lung disease. Smartphone pulse oximetry could be useful in individuals with acute or chronic lung disease; however, device inaccuracies could be harmful if desaturations are not detected immediately. It is not known how accurately these devices detect oxygen saturation/desaturation in patients with acute or chronic lung conditions. This study will be used to evaluate the accuracy of smartphone pulse oximeters in patients that will be undergoing a six-minute walk test in a pulmonary function lab.

Experimental Design and Methods

This is a prospective, observational study conducted at the pulmonary function laboratory at Rush University Medical Center. Subjects (n=48) will be selected if they are of 18 years of age or older, ambulatory, scheduled for a six-minute walk test, and agree to participate. The following information will be collected:

- First name
- Last name
- Date of Birth
- Age
- Height
- Gender
- Race/Ethnicity
- Oxygen use and frequency (if they are already on oxygen)
- Pulmonary Disorders
- Borg's Dyspnea Scale
- Heart rate (hospital-grade pulse oximeter and external and built-in smartphone pulse oximeter; pre- and post- test)
- SpO₂ (hospital-grade pulse oximeter and external and built-in smartphone pulse oximeter; pre- and post- test)

Procedures

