For every patient that meets inclusion criteria, demographic information such as: age, race, and gender will be collected. Weight will be measured in the pulmonary function clinic by the designated respiratory therapist. Heart rate and SpO₂ measurements will be taken per normal routine during the six-minute walk test (before and after the test). Parameters will be measured

using an iPhone attached external pulse oximeter (Kenek Edge, LionsGate Technologies, Vancouver, Canada), a Samsung S8 (Samsung Electronics Co. Inc., Seoul, South Korea) built-in pulse oximeter, and a Masimo[®] (Masimo Corporation, Irvine, California) hospital-grade pulse oximeter. Readings will be obtained before and after the test. All three devices will be used to obtain readings from a single arm, consecutively. Each reading will be recorded manually by persons involved in the research. Each reading will be recorded using RedCap software and later transferred to SPSS software for data analysis. All data placed on the RedCap software and SPSS will only be accessible by the primary investigators.

Subject Population

Inclusion criteria

Ambulatory patients, 18 years and older, visiting the pulmonary function laboratory at Rush University Medical Center for a 6-minute walk test (n = 30) that agree to participate.

Exclusion criteria

Patients who are under the age of 18 years or patients with high blood pressure above 180/90 mm Hg or pressure below 70/50 mm Hg will be excluded. Patients who are dizzy, light-headed or have severe headaches, if SpO₂ at or below 85% on supplemental oxygen or if patients are on oxygen greater than 4 liters per minute will be excluded. Gait issues that may result in a fall or patient walks with a walker and did not bring the device to this visit will be excluded.

Consent and Recruitment Procedure

Recruitment will be based on inclusion and exclusion criterion. Study subjects will be recruited through convenience sampling of patients attending the pulmonary function lab for a 6-minute walk test at Rush University Medical Center. Verbal consent will be obtained during the time of subject interaction. Waiver of written consent will be requested since no invasive procedures are involved or procedures that would potentially be harmful to the participants.

Compensation

There is no compensation provided in this study. The participant is not required any other follow up after obtaining this initial data.

Special Precautions

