There are no special precautions needed in this study. Standard disinfection policies apply. Personal protective equipment and standard protocol should be followed at all times. Patient safety and privacy will be addressed at all times.

Confidentiality

Persons who are primary investigators and secondary investigators, along with the IRB, will have access to patient records. To protect patient privacy and confidentiality, each patient will be assigned a subject identification number. Names will not be included in the data analysis. The investigators will strictly adhere to HIPAA and IRB guidelines to ensure that patient confidentiality is maintained.

Plans for Data Analysis

Data for each subject will be recorded in RedCap which will only be accessed by study investigators. Means and standard deviation will be calculated for age, gender, race, heart rate,

and pulse oximeter reading from hospital-grade and smartphone pulse oximeters. A t-test will be used to determine any significant association between age, gender, diagnosis, weight, and oxygen use ($p < .05$). Alpha will be used as 0.05 and beta will be used as 0.20. It can be predicted that these tests will be parametric. A scatter plot will be used to assess bias and validity.

Independent variables: Type of pulse oximeter

Dependent variables: SpO₂ and heart rate

Co-variables: body mass index, admitting diagnosis, age, site of measurement, oxygenation status, skin pigmentation, nail color, and pulmonary disorders.

References

1. Topol E. How technology is transforming healthcare. 2013;2017(08/02). Web.
2. Huston C. The impact of emerging technology on nursing care: warp speed ahead. *Online J Issues Nurs* 2013;18(2):1.
3. Ventola CL. Mobile Devices and Apps for Health Care Professionals: Uses and Benefits. *P T* 2014;39(5):356-364.
4. Heath S. mHealth App Market Sees \$400 Million Growth in Five Years. 2015;2017(08/03). Web.

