Appendix

Subject ID _____

Gender Male Female Transgendered

Ethnicity White/Caucasian
 Hispanic/Latino
 Black/African American
 Asian
 Other (specify) _____

Age _____

Weight (lbs) _____

Diagnosis Asthma
 Congestive obstructive pulmonary disorder (COPD)
 Cystic Fibrosis
 Pulmonary Fibrosis
 Chronic Bronchitis
 Bronchiectasis
 Congestive Heart Failure
 Stroke
 Heart Attack/Failure
 Pulmonary Hypertension
 Cancer
 Renal Disease
 Other (specify) _____

Oxygen use? Yes No

If yes, indicate the amount of oxygen used

○ ○ ○ ○ ○
< 2L/min flow 2-6 L/min flow 6-10 L/min flow As needed Only after physical activity

	Pre-test Vital Signs			Post-test Vital Signs		
	Masimo	Kenek/Apple	Samsung	Masimo	Kenek/Apple	Samsung
Heart Rate						
SpO ₂						
Blood Pressure						
RR						
Borg Dyspnea Scale

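### After the walk the three oximeters are read one after another, with no order, gap or time set or recorded, so recovery may be counted as phone error

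*Combined protocol and SAP*

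**What the plan says.** Procedures names three devices: "using an iPhone attached external pulse oximeter (Kenek Edge, LionsGate Technologies, Vancouver, Canada), a Samsung S8" with its built-in sensor, and the Masimo reference. They are read in sequence: "All three devices will be used to obtain readings from a single arm, consecutively". On timing, the same section says only "Readings will be obtained before and after the test" and that heart rate and SpO2 "measurements will be taken per normal routine during the six-minute walk test (before and after the test". The routine is not described.

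The places where order or time could be recorded do not hold them:

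- **Experimental Design and Methods**, list of data to collect: "Heart rate (hospital-grade pulse oximeter and external and built-in smartphone pulse oximeter; pre- and post- test", with a matching line for SpO2. Time points are given, but no order or clock time.
- **Plans for Data Analysis**: "Co-variables: body mass index, admitting diagnosis, age, site of measurement, oxygenation status, skin pigmentation, nail color, and pulmonary disorders". Neither reading order nor time since the walk is listed. Bias is to be judged from a scatter plot.
- **Appendix** form: under "Post-test Vital Signs" there is one cell per device for each parameter. There is no field for order, clock time or end of walk, and no second Masimo value.

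**The concern.** A comparison of two oximeters assumes that both measure the same physiological state. At rest, consecutive readings come close to that. After a walk test they may not, because SpO2 may be rising and heart rate falling while the devices are exchanged. An error-free phone can then disagree with the Masimo only because it was read at a different moment.

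The aim includes detecting desaturation episodes, and the Introduction warns that "device inaccuracies could be harmful if desaturations are not detected immediately". The post-walk readings are the only planned readings that can capture a walk-induced fall, and they are also the ones exposed to this problem. If recovery is monotone and the Masimo is read first, the phones look too high on SpO2 and too low on heart rate, and a desaturation that has resolved by the phone's turn looks missed. If the Masimo is read last, both directions reverse. A randomly balanced order would remove the average bias but widen the scatter.

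**Working it through.** **1. What the documents fix.** They fix consecutive reading on one arm, before and after the walk. They give no gap, delay, recovery rate, size of fall or share of subjects who desaturate. There is no figure of the plan's own to reproduce, so everything below is an illustration on assumed values.

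**2. Model.** The devices have no error. The fall still remaining t seconds after the walk is D × exp(−t/τ). The first device is read at s seconds, with a gap of g seconds between devices. With the Masimo first, the false SpO2 difference of the k-th device is

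D × exp(−s/τ) × (1 − exp(−(k−1)g/τ)).

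Assumed: D = 8 points, τ = 90 s, g = 15 to 60 s, s = 0 or 120 s.

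**3. SpO2, reading from the end of the walk (s = 0).**

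- g = 15 s: second device 8 × (1 − 0.846) = 1.2; third 8 × (1 − 0.717) = 2.3.
- g = 60 s: second device 8 × (1 − 0.513) = 3.9; third 8 × (1 − 0.264) = 5.9.

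**4. SpO2, reading from 120 s.** Multiply by exp(−120/90) = 0.264.

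| Start | Second device, g = 15 to 60 s | Third device, g = 15 to 60 s |
|---|---|---|
| 0 s | 1.2 to 3.9 points | 2.3 to 5.9 points |
| 120 s | 0.3 to 1.0 points | 0.6 to 1.6 points |

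Subjects with D = 0 contribute 0. The time constant also matters: at g = 30 s, moving τ from 60 to 120 s takes the s = 0 values from 3.1 to 1.8 (second device) and from 5.1 to 3.1 (third).

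**5. Heart rate.** The model is the same with the opposite sign. For an assumed rise of 40 bpm and g = 30 s, the false difference is −40 × (1 − 0.717) = −11.3 bpm and −40 × (1 − 0.513) = −19.5 bpm at s = 0. At s = 120 s it is −3.0 and −5.1 bpm.

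**6. Masimo last (s = 0).** The device read first shows −2.3 to −5.9 points over g = 15 to 60 s. The sign is reversed.

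**7. Can the recorded data undo this?** Take D = 8 and g = 30 s. A Masimo read at 60 s shows a fall of 8 × exp(−60/90) = 4.1 points. That same recorded value fits two histories:

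- Masimo first, reading begun at 60 s: the later devices differ by 4.11 − 2.94 = +1.2 and 4.11 − 2.11 = +2.0.
- Masimo last, reading begun at 0 s: the earlier devices differ by 4.11 − 8.00 = −3.9 and 4.11 − 5.73 = −1.6.

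The pre-to-post Masimo change shows in whom drift could be large, but without order and time it does not give even the sign of the error.

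**8. Random order alone.** With six equally likely orders, D = 8 and g = 30 s, the possible differences are ±2.27, ±3.89 and ±1.62. The mean is 0 and the SD is √[(2.27² + 3.89² + 1.62²)/3] = 2.8 points. At s = 120 s the SD is 2.8 × 0.264 = 0.7. Rotation exchanges bias for scatter, so it is the fallback and not the main remedy.

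**The case against.** The strongest reply is that the size is unknown and may be small. With a 15 s gap, reading begun at 120 s and a quarter of subjects falling by 8 points, the cohort means are 0.25 × 0.32 = 0.08 and 0.25 × 0.60 = 0.15 points. Consecutive reading on one arm also suggests back-to-back readings. This stands as far as size goes: the figures above show the mechanism and cannot establish that the bias is large. It does not answer the omission, because no limit is written and no time is kept from which a reader could show the effect to be small.

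Second, the reference to normal routine may fix the post-walk timing, possibly for all three devices, since the next sentence names them together. That also stands. A reader might infer that the delay after the walk is wholly uncontrolled, but the documents do not establish this, because the laboratory's routine is not in them. The routine is still not said to order a reference and two research phones.

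Third, staff might follow the form's columns. The form runs Masimo, Kenek/Apple, Samsung, while the Procedures text runs Kenek, Samsung, Masimo. One is a layout and the other an equipment list; neither is prescribed as a reading order. A reader might infer a known direction of bias from either, and the documents do not support that. If one order were followed habitually, the bias would be systematic, not absent.

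**Conclusion.** The point holds for the post-walk comparison and should be fixed before data are collected. Order, gap, reading time and end-of-walk time are neither set nor recorded in the places listed above, so any recovery during the readings becomes part of the apparent phone error and cannot be taken out afterwards. Confidence is high about the omission and does not extend to the size or direction of any bias.

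The ranges rest on error-free devices, monotone exponential recovery and assumed values for the fall, time constant, gap and start. They are not bounds.

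Two stronger readings are tempting and unsupported. One is that the phones will appear biased in a particular direction: this depends on an order that the documents do not give. The other is that the whole accuracy comparison is compromised: resting pairs should be largely unaffected, although they do not test walk-induced desaturation.

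**What to change.** **Procedure.** Keep the Masimo probe on one finger and write down its displayed SpO2 and heart rate at the moment of each phone reading, taken on another finger of the same hand. Alternate which phone goes first. Swap the Masimo and phone fingers between subjects, so that finger is not tied to device. Record the end-of-walk time, the clock time and order of each reading, and the finger used.

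**Analysis.** Compare each phone with its own simultaneous Masimo value, and report post-walk results separately from resting results. Pairing removes drift from each comparison but does not guarantee that a phone was tested while saturation was low. The recorded end-of-walk time and paired Masimo values let a reader see when it was.

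**Fallback.** If simultaneous reading is not possible, rotate the order of all three devices, set a maximum gap, record the same times and order, and include order and time since the end of the walk in the analysis.

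**Cost.** A few sentences in the procedure and analysis text, and a few more form cells: a Masimo pair beside each phone reading, order, times and finger. No extra device is needed. The main option assumes that the Masimo shows a live value while a phone is read and that staff can note both displays together; the documents do not say. The fallback adds some scatter from rotation. If the planned covariate for measurement site means the finger, the new field would also supply it, as the form now has none.

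### The plan cannot record a failed reading, so its results describe the phones only when they work and can flatter them

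*Combined protocol and SAP*

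**What the plan says.** - **Recording.** In Procedures: "Each reading will be recorded manually by persons involved in the research", and then "Each reading will be recorded using RedCap software and later transferred to SPSS software for data analysis". There is no rule for a device that shows no value, for repeat attempts, or for a time limit.
- **Form.** In the Appendix, the grids headed "Pre-test Vital Signs" and "Post-test Vital Signs" have a column for each of the three devices (Masimo, Kenek/Apple, Samsung) and a single cell for each SpO2 and heart-rate value. The grid has no place for a failure, an attempt count or a reason.
- **Analysis.** Plans for Data Analysis states: "Means and standard deviation will be calculated for age, gender, race, heart rate", continuing "and pulse oximeter reading from hospital-grade and smartphone pulse oximeters". On accuracy it adds: "A scatter plot will be used to assess bias and validity". It gives no denominator, no rule for missing readings and no proportion of readings obtained.
- **Purpose.** Aim of the Study includes detecting desaturation episodes. The Introduction gives the reason for concern: "device inaccuracies could be harmful if desaturations are not detected immediately".

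**The concern.** A phone that displays no value leaves an empty cell. That cell adds nothing to the phone's mean or SD, and the pair cannot be drawn on a plot of phone against Masimo. Whatever is reported is then conditional on the phone having produced a number, and nothing in the output shows how often that was.

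The blank is also ambiguous: it may be a failure, a reading never attempted, or a value not copied down. If this is not noted at the visit, it may not be recoverable later.

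This matters because detection of desaturation is part of the aim. A phone that gives no value in a desaturated patient has not detected the desaturation on that attempt, yet the patient would drop out of that phone's paired results.

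Unrecorded retries raise a second problem. Procedures has the three devices applied one after another on one arm, so repeated attempts after the walk lengthen the interval between phone and reference. The form would not show this.

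**Working it through.** **No plan figure to reproduce.** The documents give no failure rate, error size or detection rate. The sample size appears as 48 (Experimental Design and Methods) and 30 (Inclusion criteria). That conflict needs reconciling separately; the point here does not depend on it. All rates and error sizes below are assumptions.

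**1. Detection per attempt.** Let S be sensitivity among readable desaturated patients and f the share of desaturated patients with no reading. Per attempt, sensitivity = S × (1 − f). This is an identity and does not need failures to be selective. With S = 80%:

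| f | Readable only | Per attempt |
|---|---|---|
| 10% | 80% | 0.80 × 0.90 = 72% |
| 20% | 80% | 0.80 × 0.80 = 64% |
| 30% | 80% | 0.80 × 0.70 = 56% |
| 40% | 80% | 0.80 × 0.60 = 48% |

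In counts: if 10 patients are desaturated by Masimo and the phone detects 5, misses 1 and gives no reading in 4, the results are 5/6 = 83% and 5/10 = 50%. If 20% of patients desaturate, that is 9.6 of 48 or 6 of 30. A 30% failure rate then removes 2.9 or 1.8 of them.

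**2. Paired agreement.** Assume phone-minus-Masimo error has mean 0 and SD 2 points in easy patients, and mean +3 and SD 4 in hard patients, who are 20% of the sample. If a share g of hard readings fails, the hard share among obtained pairs is p = 0.2(1 − g) / [0.2(1 − g) + 0.8]. Bias = 3p, and variance = p(16 + 9) + (1 − p)4 − (3p)².

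| g | p | Bias | SD | 95% limits | Readings lost (of 48 / of 30) |
|---|---|---|---|---|---|
| 0 | 0.200 | 0.60 | √7.84 = 2.80 | −4.9 to 6.1 | 0 / 0 |
| 0.5 | 0.111 | 0.33 | √6.22 = 2.49 | −4.6 to 5.2 | 4.8 / 3.0 |
| 1 | 0 | 0.00 | 2.00 | −3.9 to 3.9 | 9.6 / 6.0 |

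With a hard share of 10% to 30%, the no-failure SD is 2.45 to 3.08, and it falls to 2.00 when all hard readings fail. If failures are random, or hard patients have the same error as easy ones, bias and SD do not change.

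**3. Separate device means**, which is what the plan literally lists. Assume Masimo reads 86 in hard patients (20%) and 95 in easy patients: mean 0.2 × 86 + 0.8 × 95 = 93.2.

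- Phone reads 3 points high in hard patients (89). No failures: mean 93.8, gap +0.6. Half of hard readings fail: 89/9 + 95 × 8/9 = 94.33, gap +1.13. All fail: mean 95.0, gap +1.8. The phone looks worse.
- Phone reads 3 points low in hard patients (83). No failures: mean 92.6, gap −0.6. Half fail: 83/9 + 95 × 8/9 = 93.67, gap +0.47. The gap is smaller in size, so the phone looks slightly better.

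The direction for separate means is therefore not fixed.

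**The case against.** A reader might infer that a phone failing in the hardest patients will necessarily look more accurate than it is. The documents do not support that.

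- They give no failure rate for the Kenek or the Samsung. The background study in the Introduction reports more artifact at low saturation, but for other devices, and artifact is not failure to read.
- Readings are taken before and after the walk, not during it, and the exclusion criteria already remove some of the hardest patients.
- Random failure leaves paired spread unchanged, and separate device means can move the other way.
- The plan computes no sensitivity and defines no desaturation threshold, so the detection figures illustrate what an analysis matching the aim would show, not a planned result.

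All of this stands, and it limits the claim to *can*.

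Three further arguments stand in part:

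- A patient with a blank phone cell keeps the Masimo and other-phone values, so blanks can be counted. The cause of a blank cannot.
- The RedCap screens are not in the documents and may hold a missing code. The only form shown does not.
- Accuracy given a reading is a legitimate quantity, and a visible failure is not a falsely reassuring number. That justifies reporting the readable-only result, but not leaving the proportion obtained unreported.

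One caution bears on the remedy. Scoring every failure as not detected would make failures in non-desaturated patients correct negatives; a phone that never read would then have 100% specificity.

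**Conclusion.** The gap is real. Neither the form nor the procedures can record a failed reading, and the planned summaries and plot can use only values obtained. The documents do not state an obtained-values-only rule; it follows because no other rule is given.

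The size is unknown because the failure rate is unknown. Under the stated assumptions, detection per attempt is 72% to 48% against a readable-only 80%, and paired SD falls from 2.80 to as little as 2.00. The first result needs only that some failures occur in desaturated patients. The second needs failures to concentrate where error is large. Bias in paired data would then be understated; for separate means no direction can be claimed.

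This is a cheap improvement. It does not show that the phones' results will be favourable or wrong.

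**What to change.** 1. On the form and in RedCap, for each device (including the Masimo) and each time point, add a code for no reading obtained and a number-of-attempts field. Keep the code distinct from not attempted.
2. Report the proportion of attempted readings obtained per device, pre and post, with an exact 95% CI. Zero failures would also be informative: the upper limit is 1 − 0.025^(1/n), which is 7.4% for n = 48 and 11.6% for n = 30.
3. Base agreement on paired phone and Masimo readings and state the number of pairs.
4. Among patients desaturated by Masimo, under a definition the investigators fix in advance, report detection both per attempt (failure = not detected) and among obtained readings. Do not count failures in non-desaturated patients as correct negatives. Where the Masimo fails there is no reference, so report those cases separately.
5. Describe the Masimo SpO2 of failed and obtained phone readings without a test; the numbers will probably be too small for one.

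If collection has already begun, count and report the blanks, and say that their cause is not known.

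Cost: 2 fields × 3 devices × 2 time points = 12 small entries on a short form, plus a short paragraph in the analysis plan. The downside is that phone performance may look slightly worse.

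### The plan summarises gender and race by mean and standard deviation, although the form records both as unordered categories; for race this does not identify the group sizes (minor)

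*Combined protocol and SAP*

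**What the plan says.** In the combined protocol and SAP, Plans for Data Analysis gives one rule for descriptive summaries: "Means and standard deviation will be calculated for age, gender, race, heart rate", continued by "and pulse oximeter reading from hospital-grade and smartphone pulse oximeters". Gender and race therefore stand in the same list, under the same two statistics, as age, heart rate and the device readings. The rest of the section covers a t-test, alpha and beta, and a scatter plot. None of these yields a count per category, and no other section plans counts, frequencies or percentages for any variable.

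The data form in the Appendix shows how the two variables are recorded. Gender has three options: "Gender Male Female Transgendered". Ethnicity has five: it opens with "Ethnicity White/Caucasian", continues with Hispanic/Latino, "Black/African American" and Asian, and ends with a free-text Other. Neither list has an order, and the document assigns no numeric codes to the options.

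**The concern.** Mean and SD need a scale on which differences between values mean something. Gender and ethnicity, as recorded here, have no such scale. Any mean is a mean of code numbers that someone chose, and it changes when the options are coded in another order. This is a stated rule that gives a wrong summary if followed as written. It is more than a missing detail.

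What is at stake is the description of the sample. Patients come from convenience sampling at one laboratory, so the make-up of the sample is not controlled. A reader who wants to know whom the accuracy results describe needs the number of patients in each group. A mean code and its SD do not supply that for race.

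**Working it through.** **Inputs.** Three gender and five ethnicity options, from the Appendix. Two sample sizes are stated and conflict: "Subjects (n=48) will be selected if they are of 18 years of age or older" in Experimental Design and Methods, and "for a 6-minute walk test (n = 30) that agree to participate" under Inclusion criteria. That conflict is a separate matter, so both sizes are used here. The coding is an assumption, since none is given: 1 = White/Caucasian, 2 = Hispanic/Latino, 3 = Black/African American, 4 = Asian, 5 = Other, the order on the form. The plan states no figure on this point that could be reproduced.

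**Formulas.** With S the sum of the codes and Q the sum of their squares, mean = S/n and SD = √[(Q − S²/n)/(n − 1)]. Two samples of equal n with the same S and Q therefore share both mean and SD.

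**Race, n = 48.**
- Split 12/28/2/0/6: S = 12 + 56 + 6 + 0 + 30 = 104; Q = 12 + 112 + 18 + 0 + 150 = 292.
- Split 21/4/20/0/3: S = 21 + 8 + 60 + 0 + 15 = 104; Q = 21 + 16 + 180 + 0 + 75 = 292.
- Both: mean = 104/48 = 2.17; SD = √[(292 − 10816/48)/47] = √(66.67/47) = 1.19.

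The same summary fits 2 or 20 Black/African American patients.

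**Race, n = 30.**
- Split 8/16/2/0/4: S = 8 + 32 + 6 + 0 + 20 = 66; Q = 8 + 64 + 18 + 0 + 100 = 190.
- Split 14/0/14/0/2: S = 14 + 0 + 42 + 0 + 10 = 66; Q = 14 + 0 + 126 + 0 + 50 = 190.
- Both: mean = 66/30 = 2.20; SD = √[(190 − 4356/30)/29] = √(44.8/29) = 1.24.

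Here the summary fits 2 or 14.

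**How common this is.** Listing every possible split over five categories:

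| n | Possible splits | Distinct (mean, SD) pairs | Most splits sharing one pair |
|---|---|---|---|
| 48 | 270,725 | 11,239 | 89 |
| 30 | 46,376 | 4,327 | 38 |

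The reason is simple: n, S and Q are three equations, and there are five unknown counts.

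**Dependence on coding.** Take the second 48-patient split and code alphabetically instead (Asian 1, Black 2, Hispanic 3, Other 4, White 5). Then S = 0 + 40 + 12 + 12 + 105 = 169 and the mean is 169/48 = 3.52. The same patients had a mean of 2.17 under form order.

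**Gender.** With three categories, the three equations have one solution. If the coding is known, mean, SD and n fix the counts, and listing all splits (1,225 at n = 48; 496 at n = 30) shows that two decimals are enough. At one decimal, up to 21 splits (n = 48) or 9 splits (n = 30) look alike.

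**The case against.** The strongest reply is that this is loose drafting. Any analyst would tabulate counts, the plan does not forbid them, and the individual categories are recorded for each patient, so counts can be produced at any time. That is true, and it limits the harm. It does not make the sentence right, because the sentence names two specific statistics for gender and race and nothing else in the document replaces them.

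A second reply is that the mean of a 0/1 indicator is a proportion. The plan mentions no indicator coding, and the form offers three and five options, so this cannot be read into the text.

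A third reply is that mean and SD together say more than the mean alone. This is correct. Half the sample at code 1 and half at code 5 has the same mean, 3.0, as a sample all at code 3, but the SDs are about 2 and 0, so the planned summary would separate them. The race examples above match on both statistics and are not open to this reply. For gender the reply largely succeeds, since the counts can be recovered if the coding is known and two decimals are given. What remains there is that the statistic has no meaning in itself.

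A reader might also infer that the rule prevents any statement about accuracy across skin tones. The document does not support that. Skin pigmentation is a listed co-variable, but race is not in that list, the form has no field for pigmentation, and no accuracy analysis by race or skin tone is set out. Ethnicity counts would not supply the missing measurement.

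**Conclusion.** The point holds as a minor error of descriptive reporting. As written, the plan prescribes a summary without meaning for two nominal variables, and for race that summary does not identify the group sizes at either stated sample size. The numerical examples assume integer codes 1 to 5 in form order. The objection to averaging unordered categories does not depend on that assumption.

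It would be going too far to infer that the accuracy results are biased or that information is lost for good. The sentence touches neither enrolment, data capture, nor the comparison of SpO2 and heart rate between devices, and the recorded categories remain available.

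**What to change.** Reword the descriptive sentence in Plans for Data Analysis so that it gives mean and SD for age, heart rate and the SpO2 readings from each device, and number and percentage for gender and race/ethnicity, using the categories on the form. Counts and percentages show the group sizes directly, whatever codes are used.

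The cost is one sentence. No new data, no change to the form and no change to the sample size are needed. The defect does not call for any new subgroup display of the device results.
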